**Document date: 10.01.2020**

**NCT: NCT03837028.**

## **The effect of being diagnosed with human papillomavirus infection on women's sexual lives**

### **Materials and Methods**

The present prospective observational study was conducted with women referred to our gynecology outpatient clinic upon being diagnosed with an HPV infection by the community based cervical cancer screening program. After obtaining the ethical approval (approval number: 2017/33) from our hospital's local ethics committee, the patients who had been diagnosed with a high-risk HPV (HPV 16, 18, 31, 33, 35, 39, 45, 51, 52, 56, 58, 59, 68, 69, and 82) infection for the first time in their lives and who were sexually active and in the reproductive period were included in this study. All the patients were  $\geq 30$  years old (cervical cancer screening with co-test starts at the age of 30 years in Turkey).

Post-menopausal women, and patients with the low-risk HPV genotypes (HPV 6 or 11), sexual penetration disorders, chronic systemic diseases, a sexual abuse history, or a prior HPV infection, and those under any antidepressant medication or diagnosed with psychiatric disorders were excluded from the study. Additionally, patients who did not agree to participate in the study after reading the informed consent form and those who did not come for the follow-up visit were also excluded.

The patients who met the inclusion criteria were informed about the details of the study and were asked whether they would have liked to participate in this study. Written informed consent was obtained from all the patients who agreed to do so. The sociodemographic data of these patients, such as pregnancy, parity, Body Mass Index (BMI), educational level, and marital status were recorded. We had the participants filled out the FSFI and BAI questionnaires at the first visit to assess the initial sexual functions and anxiety levels of the women. Then the participants were informed about their co-test results and were divided into four groups according to their HPV genotypes and cytology results as follows: Group 1, HPV 16/18-positive and normal cytology; Group 2, HPV 16/18-positive and abnormal cytology; Group 3, non-16/18 HPV-positive and abnormal cytology; and Group 4, non-16/18 HPV-positive and normal cytology.

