### **Statistical Analysis**

Data analysis was performed by using SPSS (IBM SPSS Statistics for Windows, Version 20.0. Armonk, NY: IBM Corp.). A one-sample Kolmogorov–Smirnov test was performed to analyze the distribution of the clinical variables. The frequencies and percentages of the categorical variables and the mean, standard deviation, median, and range values of the continuous and ordinal variables are presented. The study groups were compared using Oneway analysis of variance (ANOVA) and the Kruskal Wallis H tests for the parametric and non-parametric

variables, respectively. The Bonferroni correction was performed for posthoc analyses of the significant differences in the second-visit BAI score among the study groups. The Wilcoxon rank test was used for the comparison of the BAI and FSFI scores at the first and second visits. For all the calculations, a p-value of  $< .05$  was considered statistically significant.

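### The parametric group comparison is an equal-variance one-way ANOVA on four observational groups of unplanned size, with no unequal-variance step; its effect on second-visit BAI is conditional

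*Combined protocol and SAP*

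**What the plan says.** Materials and Methods describes a prospective observational study in which participants "were divided into four groups according to their HPV genotypes and cytology results as follows": HPV 16/18 or other high-risk types, each with normal or abnormal cytology. No total sample size, group size or allocation ratio is given. Women who miss the follow-up visit are excluded, so the analysed group sizes also depend on attendance.

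Statistical Analysis then sets out four relevant elements:

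- Distribution check: "A one-sample Kolmogorov–Smirnov test was performed to analyze the distribution of the clinical variables".
- Group comparison: "The study groups were compared using Oneway analysis of variance (ANOVA) and the Kruskal Wallis H tests for the parametric and non-parametric" variables, respectively. By implication, the distribution check decides which test a variable receives.
- Multiplicity: "The Bonferroni correction was performed for posthoc analyses of the significant differences in the second-visit BAI score among the study groups".
- Threshold: "For all the calculations, a p-value of $< .05$ was considered statistically significant".

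The section names no equal-variance check, no Welch or Brown–Forsythe ANOVA and no unequal-variance post-hoc test. SDs appear only as descriptive output. It does not say which omnibus test second-visit BAI receives, or what kind of pairwise test the Bonferroni correction is applied to.

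**The concern.** The ANOVA F test divides between-group variation by one pooled within-group variance. If groups differ in both size and spread, the large groups dominate that pooled figure while the small groups contribute disproportionately to the numerator. The test then rejects too often when the small groups are the variable ones, and too seldom when the large groups are. Equal group sizes largely protect against this, but this design does not provide them.

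Equal spread is not assured either. The groups receive different clinical news, and groups 1 to 3 go directly to colposcopy while group 4 goes only on suspicion of a lesion. A normality check does not detect unequal SDs. For any variable sent to ANOVA, a p-value below .05 may therefore not carry a 5% error rate.

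**Working it through.** **Inputs from the documents.** Four groups (k = 4); threshold 0.05; ANOVA for parametric variables and Kruskal–Wallis for the rest; no group sizes, SDs or variance step.

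**Inputs assumed.** Normal scores, equal true means, and the group sizes and SDs shown below. Sizes and SDs are listed in the order of groups 1 to 4.

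**Step 1: reproduce the nominal 5%.** With equal SDs, simulation of the classical F test (100,000 runs per setting) gave 4.9–5.2% at all five sets of sizes, balanced and unbalanced. The stated level is correct when the equal-variance assumption holds.

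**Step 2: why unequal SDs matter only with unequal sizes.** With equal means and N = Σnᵢ, the expected mean squares are:

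- Between groups: Σ(1 − nᵢ/N)σᵢ² / (k − 1)
- Within groups: Σ(nᵢ − 1)σᵢ² / (N − k)

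With equal sizes both reduce to the average variance, so their ratio is 1. Two unequal cases:

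- Sizes 50/15/15/120, SDs 6/12/12/6 (N = 200). Between: (0.75×36 + 0.925×144 + 0.925×144 + 0.40×36)/3 = 307.8/3 = 102.6. Within: (49×36 + 14×144 + 14×144 + 119×36)/196 = 10,080/196 = 51.4. The ratio is 2.0, so F is inflated about two-fold with no true difference.
- Sizes 40/20/20/60, SDs 12/8/8/12 (N = 140). Between: (0.7143×144 + 0.8571×64 + 0.8571×64 + 0.5714×144)/3 = 294.9/3 = 98.3. Within: (39×144 + 19×64 + 19×64 + 59×144)/136 = 16,544/136 = 121.6. The ratio is 0.81, so F is deflated.

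**Step 3: false-positive rates, first set of assumptions.** Sizes 40/20/20/60, 30/15/25/70, 40/15/20/100 and 50/15/15/120.

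| SD pattern | ANOVA | Welch |
|---|---|---|
| 8/10/10/8 to 6/12/12/6 (smaller groups more variable, ratio 1.25 to 2) | about 7.5–26% | about 5% |
| 12/8/8/12 (larger groups more variable, ratio 1.5) | about 2–3% | about 5% |
| Unequal SDs, 30 per group | about 5–6% | about 5% |

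**Step 4: second set of assumptions.** Sizes 25/15/20/60, 40/20/30/90, 20/10/15/75 and 50/25/40/185, with 30 per group as the balanced case. ANOVA and Welch used 100,000 runs per setting; Kruskal–Wallis used 4,000.

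| Setting | ANOVA | Welch | Kruskal–Wallis |
|---|---|---|---|
| Smaller groups more variable, ratio 1.5 | 9.5–12.4% | 4.9–5.4% | 7.4–8.2% |
| Smaller groups more variable, ratio 2 | 13.4–19.0% | 5.1–5.3% | 8.9–11.5% |
| Larger groups more variable, ratio 1.5 | 1.6–2.4% | 4.9–5.2% | 2.6–3.6% |
| Larger groups more variable, ratio 2 | 0.6–1.4% | 4.9–5.1% | 1.6–2.8% |
| 30 per group, ratio 1.5 to 2 | 5.2–5.9% | 4.9–5.1% | 3.8–5.5% |

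Across both sets, Kruskal–Wallis drifts to about 6–14% in one direction and about 2–4% in the other.

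**Step 5: the pairwise step under the fix.** Four groups give six pairs, so Bonferroni uses 0.05/6 = 0.0083 per pair. Welch t tests at that level held the family-wise error at 3.8–4.2% in every setting of Step 4.

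**Step 6: power cost.** With means 10/15/15/10 and a common SD of 9, moving from ANOVA to Welch lowered omnibus power from 71.1% to 69.9%, 68.6% to 66.9% and 68.4% to 65.3%: losses of 1.2, 1.7 and 3.1 points.

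**The case against.** The strongest reply is that the outcome of most interest may never reach ANOVA. The plan compares BAI and FSFI across visits with a Wilcoxon test, which suggests that both were treated as non-parametric, and between groups that points to Kruskal–Wallis. BAI is a sum of 21 items scored 0–3, so it is bounded at 0–63. A normal score with mean 8 and SD 8 would put 15.9% of values below zero, so real scores with those moments would be skewed. In a check with rounded, capped gamma scores (an assumed shape), a pooled Kolmogorov–Smirnov test rejected normality in 87.5–100% of runs. ANOVA may then apply mainly to background variables such as BMI. This stands, and it makes the effect on BAI conditional.

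A reader might also infer that the plan runs pooled-SD Bonferroni t tests, and so carry the ANOVA error rates over to the BAI pairwise results. The documents do not support that. Bonferroni is tied only to the second-visit BAI post-hoc analysis, and no form of pairwise test is stated; rank-based pairs fit the wording equally well.

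Finally, the size of the error rests on assumptions. No passage says that the abnormal-cytology groups are smaller or more variable, and both imbalances are needed to produce the large figures. That also stands.

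These replies do not remove the gap. ANOVA remains an active branch with no protection against unequal SDs, and Kruskal–Wallis drifts from 5% in the same settings.

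**Conclusion.** The concern holds in a limited form. For any variable judged parametric, the plan relies on equal variances across four groups whose sizes are not set by design, and it neither checks nor relaxes that assumption. If sizes and SDs both differ as in the first set of assumptions, the error at nominal 5% is about 7.5–26% or about 2–3%, depending on which groups are more variable, against about 5% for Welch. With equal sizes it stays near 5–6%.

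This is a possible distortion, not a demonstrated one: the documents give neither group sizes nor SDs, and the figures assume normal scores. For second-visit BAI the ANOVA result applies only if that score is in the parametric branch, which the text leaves open. It would go too far to conclude that the BAI comparison has an inflated error rate.

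**What to change.** - Replace one-way ANOVA with Welch's ANOVA for variables in the parametric branch.
- State which omnibus test and which post-hoc method apply to second-visit BAI. If it is in the parametric branch, use Games–Howell, or Welch t tests with Bonferroni over the six pairs.
- If second-visit BAI is analysed by Kruskal–Wallis, read a significant result as a difference in distribution unless the group spreads are similar. This is a caution on interpretation; it does not restore the 5% level.
- Report n and SD for each group, and mean differences with 95% CIs, so that readers can judge whether sizes and spreads differ enough to matter.

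The textual change is a few sentences. The statistical cost is about 1–3 points of omnibus power if the SDs are in fact equal. The section is written in the past tense, so the change may also mean re-running the parametric comparisons.
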